## 1. SUMMARY OF AMENDMENT HISTORY

The original protocol (Version 1.0), dated 24 Sep 2008, was globally amended 5 times. There was also 1 country-specific amendment for the Czech Republic and 4 non-substantial amendments (administrative letters). Brief summaries of the changes are outlined in the sections below.

A country-specific amendment for Russia was also developed; this amendment is not included in this document or the clinical study report as the study was never conducted in Russia.

## 2. AMENDMENT 1, PROTOCOL VERSION 2.0 (16 APRIL 2009)

FDA feedback received from a Special Protocol Assessment (SPA) request necessitated an amendment to Protocol 093-045 version 1.0 (25 July 2008). Based on amended Protocol 093-045, version 2.0 (04 March 2009) the following changes were made to the protocol:

- Throughout the text, new wording “not well controlled by” replaced the previous wording “unresponsive to” so as not to confuse subjects enrolled in the present study with patients who have become refractory to other AEDs.
- Allowance of lorazepam, other benzodiazepines, and newer generation sleep medications as occasional sleep medicines (up to once a month).
- Clarified provision of rescue medication (lorazepam would be provided locally by investigator as standard-of-care and not through the sponsor).
- Addition of testing for creatinine phosphokinase (indicator of muscle lysis caused by seizure activity); and elimination of testing for tricyclic antidepressant as part of urine drug screen.
- Addition of diazepam rectal gel dosing chart.
- Replacement with new versions of medical events calendar, seizure diary, and QOLIE-31 scale.
- Elimination of criteria for independent blinded rater for the MADRS scale (as improvement in MADRS was not a primary endpoint of the study and this requirement would be better suited for clinical studies of depression. Suicidality would be better assessed through the C-SSRS).

### **3. AMENDMENT 2, PROTOCOL VERSION 3.0 (24 JULY 2009)**

Protocols 093-045 (Version 2.0, 04 March 2009) and 093-050 (Version 2.0, 16 April 2009) were reviewed by Health Canada as part of a CTA application and at an Investigator's meeting held in the USA (3-5 June 2009). Based on feedback received from the regulatory authority and by US investigators the following major changes were made to the protocol:

- Removal of requirement that efficacy and safety assessments must occur in a specific order. However, vital signs and ECGs were to be collected prior to blood draws.
- Further clarification regarding permitted use of benzodiazepines as sleeping medications.
- Addition of dose adjustment requirement for concomitant medications whose plasma levels may increase after taper/discontinuation of certain enzyme inducing antiepileptic drugs.
- Allowance of change in setting of vagal nerve stimulator in subjects with a clinically significant worsening of seizures or increase in seizure frequency.
- In cases of subject discontinuation/withdrawal due to need for >2 AEDs, provision of instructions that study drug taper schedule would be at Investigator's discretion and an unscheduled visit to record adverse events and return unused study drug.
- Simplification of seizure diary.

### **4. NON-SUBSTANTIAL AMENDMENT 1 (22 APRIL 2010)**

The purpose of this non-substantial amendment (administrative letter) was to notify the Investigators of the following administrative clarifications to Sepracor Protocol 093-050 (Version 3.0, 24 July 2009):

- The EudraCT number for this study is 2010-018684-42. Sites were provided with a self-adhesive label citing this EudraCT number that should have been affixed to the title page of the protocol.
- The telephone and fax numbers for 24-hour SAE Reporting was updated.
- Section 7.3.3, Health Outcomes Assessments: The site staff could use the review of subject entries in the Medical Events Calendar (MEC) as a source to determine if further data about the subject's utilization of health care services should be obtained.

## 5. AMENDMENT 3, PROTOCOL VERSION 4.0 (09 JUNE 2010)

Based on continued feedback from the contract research organization and investigative sites enrolling subjects the following changes/clarifications were made to the protocol:

- Addition of information (in table format) on diazepam doses and formulations when used as rescue medication in countries where lorazepam as rescue medication was not available.
- Addition of information (in table format) on diazepam doses and formulations when used as emergency medication in countries where Diastat® (diazepam rectal gel) as emergency medication was not available.
- Clarification that the Medical Events Calendar (MEC) could have been used as an additional tool for collection of health outcomes assessments.
- Addition of trazodone as allowed medication.
- Addition of marijuana as a disallowed medication.
- Clarification that the PI or designee must provide a prescription for diazepam when used as emergency or rescue medication (formulation/dose as listed in Appendices XII and XIII).
- Addition of telephone and fax numbers for 24-hour SAE reporting in Europe.
- Addition of the Eudra CT number.
- Change in responsible physician.
- Increase in sample size from 270 to 348 subjects as a result of the increase in sample size for Protocols 093-045 and 093-046.

## **6. AMENDMENT 4, PROTOCOL VERSION 5.0 (17 AUG 2010)**

The sponsor extended the current study duration to beyond 1-year. This allowed subjects who demonstrated clinical benefit over a 1-year period to continue receiving study drug beyond 1-year. There was no change in sample size or change in study drug dosing resulting from the extended duration of study. The protocol has been amended to incorporate the following major changes:

- A post-1-year period that would follow the 1-year period. The post-1-year period would continue until the subject discontinues study, the study drug becomes clinically available in the subject's locale, or the sponsor terminates the study drug clinical development program.
- Addition of new post-1-year primary objective and 2 new post-1-year secondary objectives.
- Addition of a new post-1-year endpoint.
- Addition of post-1-year Patient Global Impression (PGI) scale for assessing improvement in disease.
- Addition of a continuation criterion for subjects who choose to continue into the post-1-year part of the study.

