## 3. Study design

### 3.1. General Description

This study is a long-term, multicenter, open-label, safety extension study in male and female subjects (aged 16 to 70 years, inclusive) with partial onset seizures who have just completed, discontinued, or exited the 18-week treatment phase of Protocols 093-045 or 093-046. The initial study duration is 1-Year Open-Label Period with the option of continuing study drug treatment Post-1-Year Open-Label Period until a subject discontinues study, the study drug becomes clinically available in the subject's locale, or the sponsor terminates the study drug clinical development program.

This study will evaluate the safety and maintenance of effect of long-term eslicarbazepine acetate treatment at flexible doses in the range of 800 mg to 2400 mg once-a-day (QD) over a 1-Year Open-Label Period and a Post-1-Year Open-Label Period.

[figure not shown]

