**8. Treatment retention time (time to withdrawal due to lack of efficacy or adverse events).**

If a subject's reason for withdrawal from 1-Year Open-Label Period included: withdrawal of consent, lost to follow-up, physician decision or other, then it will be assumed the subject terminated due to lack of efficacy. For subjects that discontinue due to adverse event or lack of efficacy, the treatment retention time during the 1-Year Open-Label Period will be calculated as the date of last known dose during the 1-Year Open-Label Period minus the date of the first dose of eslicarbazepine acetate monotherapy in protocol 093-045 or 093-046 (Visit 6/Week 8), plus 1. The time may include taking eslicarbazepine acetate concomitantly with other AEDs.

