## **4. Treatment retention time**

If a subject’s reason for withdrawal from Post-1-Year Open-Label Period included: withdrawal of consent, lost to follow-up, physician decision or other, then it will be assumed the subject terminated due to lack of efficacy. For subjects that discontinue due to adverse event or lack of efficacy, the treatment retention time during Post-1-Year Open-Label Period will be calculated as the date of last known dose during Post-1-Year Open-Label Period minus the date of the first dose of eslicarbazepine acetate monotherapy in protocol 093-045 or 093-046 (Visit 6/Week 8), plus 1. The time may include taking eslicarbazepine acetate concomitantly with other AEDs.

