### **7.2 Disposition of Subjects**

The number and percentage of subjects who entered 1-Year Open-Label Period, who completed the 1-Year Open-Label Period, who discontinued during 1-year Open-Label Period (including reasons for discontinuations), who completed 1-Year Open-Label period but did not enter the Post-1-Year Open-Label Period, entered Post-1-Year Open-Label Period, and discontinued early (including reasons for discontinuations) for Post-1-Year Open-Label Period, and who completed Post-1-Year Open-Label Period will be summarized. The number and percentage of subjects who were in actual monotherapy used subgroup and PP population will be also summarized respectively.

Subject disposition will be summarized for the ITT population.

Listing of subject disposition will be provided.

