**Treatment retention**

Kaplan Meier methods will be used to estimate the median retention time (and 95% CI) on eslicarbazepine acetate for subjects who discontinued early due to adverse event(s) or lack of efficacy for both 1-Year Open-Label Period and Post-1-Year Open-Label Period.

For 1-Year Open-Label Period, subjects who discontinued the study not due to those reasons (i.e. protocol deviation) as defined in Section 5.2.2 will be censored at the date of the last known dose during 1-Year Open-Label Period. Subjects who were still taking eslicarbazepine acetate at the end of the 1-Year Open-Label Period of study will be censored at the last dose of the 1-Year Open-Label Period.

For Post-1-Year Open-Label Period, subjects who discontinued the study not due to those reasons (i.e. protocol deviation, study drug became available in subject's locale, and sponsor terminates clinical study) as defined in Section 5.2.3 will be censored at the date of the last known dose during Post-1-Year Open-Label Period. Subjects who were still taking eslicarbazepine acetate at the end of the Post-1-Year Open-Label Period of study will be censored at the last dose of the Post-1-Year Open-Label Period.

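### A stop at Visit 7 for lack of efficacy or side effects is an event in neither retention curve, so the Post-1-Year curve, if limited to entrants, overstates long-term retention

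*Protocol*

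**What the plan says.** **Continuation past Visit 7.** The log entry for Amendment 4 (Protocol, section 6) gives the purpose of the extension as "This allowed subjects who demonstrated clinical benefit over a 1-year period to continue receiving study drug beyond 1-year" and lists "Addition of a continuation criterion for subjects who choose to continue into the post-1-year part of the study". The wording of that criterion is not in the supplied text. The SAP (3.1) describes a one-year study "with the option of continuing study drug treatment Post-1-Year Open-Label Period". A footnote to the SAP schedule (5.1) has drug dispensed at Visit 7 only to those who continue.

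**1-Year retention.** SAP 5.2.2 item 8 defines the event: "For subjects that discontinue due to adverse event or lack of efficacy, the treatment retention time during the 1-Year Open-Label Period will be calculated". Lack of efficacy is also assumed when the "reason for withdrawal from 1-Year Open-Label Period included: withdrawal of consent, lost to follow-up, physician decision or other". Under Treatment retention in SAP 7.6, "Subjects who were still taking eslicarbazepine acetate at the end of the 1-Year Open-Label Period of study will be censored" at the last dose of that period.

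**Post-1-Year retention.** SAP 5.2.3 item 4 applies the same convention when the "reason for withdrawal from Post-1-Year Open-Label Period included" one of those reasons. The time runs from the first monotherapy dose in the parent study (Visit 6/Week 8) to the last dose in the Post-1-Year period.

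**Disposition.** SAP 7.2 has a row for subjects "who completed 1-Year Open-Label period but did not enter the Post-1-Year Open-Label Period". It asks for reasons on the two discontinuation rows but not on this one.

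**The concern.** The two retention analyses meet at Visit 7, and neither counts as a failure a subject who stops there for poor effect or side effects. That is the kind of failure the endpoint is named for. It also sits oddly with the SAP's own cautious convention: a physician decision or consent withdrawal shortly before Visit 7 counts as lack of efficacy, while the same decision at Visit 7 counts as nothing.

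What is at stake is the reading of long-term retention. Maintenance of effect over both periods is a secondary objective (SAP 2.2), and seizure diaries stop at Visit 7 (SAP 5.2.1), so retention is one of the few efficacy measures that cover both periods. The Post-1-Year curve starts its clock in the parent study and therefore looks like retention from the start of monotherapy. If only entrants contribute, it is conditional on having passed Visit 7.

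**Working it through.** The documents state no retention rate, event count or power for this endpoint, so there is no plan figure to reproduce. The check has four steps.

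**1. Rule trace** for a subject dosed through Visit 7 who then stops for lack of benefit or side effects:

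| Analysis | Rule | Result |
|---|---|---|
| 1-Year retention (SAP 5.2.2 item 8, 7.6) | On drug at period end: censored, no exception | No event |
| Post-1-Year retention (5.2.3 item 4) | Needs a last dose in, and a withdrawal reason from, that period | No time derivable |
| Entire open-label period (5.2.4) | Only QOLIE-31 and MADRS listed | No retention analysis |
| 1-Year completion (5.2.2 item 7) | Completed Visit 1 to Visit 7 | Completer |
| Disposition (7.2) | Own row, no reasons requested | Counted, unexplained |

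The subject adds no event to either curve.

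**2. What an entrants-only curve shows.** Monotherapy starts at Week 8 of an 18-week parent study. For a subject who completed the parent study, Visit 7 therefore falls about 18 − 8 + 52 = 62 weeks after the clock starts, ignoring any gap between studies. No entrant can have an event before then, so the curve stays at 100% to about week 62.

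**3. Size.** Let S be retention at Visit 7 under the SAP rules, and g the share of those reaching Visit 7 who stop there for lack of efficacy, an adverse event or an unmet criterion. Retention just after Visit 7 is S × (1 − g). With S = 70% (assumed):

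- g = 5%: 0.70 × 0.95 = 66.5%
- g = 10%: 0.70 × 0.90 = 63%
- g = 20%: 0.70 × 0.80 = 56%

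The same check in whole subjects takes N = 348 (the planned number in Amendment 3, assumed all enrolled), no other censoring, and 20%, 30% or 40% with events before Visit 7 (assumed):

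| Events before Visit 7 | Reach Visit 7 | SAP rules | g = 5% | g = 10% | g = 20% |
|---|---|---|---|---|---|
| 70 | 278 | 79.9% | 75.9% | 71.8% | 63.8% |
| 104 | 244 | 70.1% | 66.7% | 63.2% | 56.0% |
| 139 | 209 | 60.1% | 57.2% | 54.0% | 48.0% |

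For example, 104 + 24 = 128 events gives (348 − 128)/348 = 63.2%. The gap runs from 2.9 points (60.1 − 57.2) to 16.1 points (79.9 − 63.8).

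The planned statistic is the median. An entrants-only median is reached when half the entrants have failed. In the whole population it is reached when retention among entrants falls to 0.5/[S(1 − g)]. With S = 70% that is 0.5/0.70 = 71.4% for g = 0, 0.5/0.63 = 79.4% for g = 10% and 0.5/0.56 = 89.3% for g = 20%, so the median comes earlier.

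**4. Where the event may safely be placed.** S × (1 − g) needs the continuers to remain at risk past Visit 7. In the 1-Year curve they are censored at their own last 1-Year dose, and those dates differ between subjects. Making Visit 7 stops events there puts events into a vanishing risk set. A simulation took 348 subjects, 104 events before Visit 7, g = 10% and a 7-day standard deviation in exit day (all assumed). Final 1-Year retention averaged about 40% instead of 63%, and a spurious median appeared in about 71% of runs. In a curve that follows continuers past Visit 7, the estimate is (348 − 128)/348 = 63.2%.

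**The case against.** The strongest case on the other side is that the SAP does what it says. The 1-Year endpoint is retention during that year, and a subject dosed to Visit 7 was retained for it. **This stands.** A reader might infer that year-1 retention is overstated, or that these stops should become events in the 1-Year curve. The documents do not support the first, and step 4 shows that the second would do harm.

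A reader might also infer that only subjects with clinical benefit may continue. That rests on one sentence in an amendment log, which explains the extension and does not say only. The SAP calls continuation an option, and the criterion's wording is not supplied. The point does not need that reading: a subject who declines to continue because of poor effect or side effects follows the same path through the rules.

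Nor are these subjects lost from every table. They have a disposition row. If the Post-1-Year completion rate (5.2.3 item 2) uses the full ITT population as worded, they are non-completers there. If a site recorded lack of efficacy as the reason for withdrawal from the 1-Year period, 5.2.2 item 8 would make it an event while 7.6 would censor it, and the SAP does not say which prevails.

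Two further limits stand. The SAP uses ITT for all efficacy analyses and states no entrants-only population, so absence from the Post-1-Year curve is inferred from the definition of the time. And this is a descriptive, single-arm study with a safety primary objective, so no formal test is affected.

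**Conclusion.** The concern holds in a limited form. As written, non-continuation at Visit 7 for lack of efficacy, an adverse event or an unmet continuation criterion is a retention event in neither curve. Retention during year 1 is sound. The Post-1-Year curve, if limited to entrants, omits all failures up to and at Visit 7 while its clock starts in the parent study, so it overstates long-term retention.

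The Visit 7 stops alone account for 3.5, 7 or 14 points at g = 5%, 10% or 20% from an assumed 70%, and for 2.9 to 16.1 points across the scenarios shown. Both g and the retention level are assumptions. If g is near zero, only the conditioning on entry remains. The existence of the gap rests on the rule trace and not on these figures.

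**What to change.** 1. Leave the 1-Year curve as it is, censored at Visit 7.
2. In SAP 5.2.3 item 4 and 7.6, estimate long-term retention in the full ITT population over the entire open-label period. Keep the 1-Year events, follow continuers past Visit 7, and count non-entry for lack of efficacy, an adverse event or an unmet continuation criterion as an event at the last dose.
3. Censor completers who had no option to continue, for example because Version 5.0 was not yet in force at the site, the drug had become available locally or the sponsor had terminated the study.
4. For non-entry due to consent, physician decision, other or unknown reasons, apply the SAP's lack-of-efficacy convention in one analysis and censor in a sensitivity analysis.
5. State which rule prevails when lack of efficacy is recorded as the 1-Year withdrawal reason at Visit 7.
6. State the risk set of any Post-1-Year curve that is kept.
7. In 7.2, tabulate reasons for completing the year without entering the next period.

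The cost is SAP wording, one derivation and one table row. The long-term figure will be less favourable. The documents do not show that a reason for non-entry was recorded for every completer, so some may be missing; item 4 shows how much that matters.

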## **7. CZECH REPUBLIC-SPECIFIC AMENDMENT 1, PROTOCOL 5.1 (16 NOVEMBER 2010)**

As of October 2010, Sepracor Inc. has changed its name to Sunovion Pharmaceuticals Inc. Edits to the protocol were made to reflect the name change.

## **8. NON-SUBSTANTIAL AMENDMENT 2 (12 DECEMBER 2011)**

The purpose of this letter was to notify the Investigators of the administrative change to Sunovion Pharmaceuticals Inc. Protocol 093-050 (Version 5.0, 17 Aug 2010, Czech Republic-Specific Local Amendment Version 5.1, 16 Nov 2010, and Russia-specific Protocol Version 5.1, 14 Jan 2011).

The contact for reporting of SAEs, pregnancies, and any other immediately reportable events was updated.

## **9. NON-SUBSTANTIAL AMENDMENT 3 (03 DECEMBER 2012)**

The purpose of this non-substantial amendment (administrative letter) was to notify the Investigators of the following administrative changes to Sunovion Pharmaceuticals Inc. Protocol 093-050 (Version 5.0, 17 Aug 2010; Czech Republic-specific Local Amendment Version 5.1, 16 Nov 2010; and Russia-specific Protocol Version 5.1, 14 Jan 2011):

- For clarification, all pregnancy tests (urine and serum) were to be conducted in female subjects of child bearing potential ONLY. The definition of child-bearing potential was provided in Section 8.1 (Subject Inclusion/Exclusion Criteria) of the protocol.
- Effective 03 Dec 2012 serious adverse events, (SAEs), pregnancies, and any other immediately reportable events for Protocol 093-050 were to be reported to PPD Pharmacovigilance (PVG).

## **10. AMENDMENT 5, PROTOCOL VERSION 6.0 (07 JUNE 2013)**

The protocol was amended to remove the following post-1-year EOS/ET visit assessments: clinical laboratory evaluations (performed only if clinically indicated), coagulation testing, thyroid panel, lipid panel, bone turnover markers, and serum pregnancy tests. The post-1-year EOS/ET 12-lead ECG assessment was to be performed only if clinically indicated. The Sponsor determined that these assessments do not contribute additional information needed to evaluate the overall safety profile of eslicarbazepine acetate.

In addition, updates outlined in non-substantial amendments (administrative letters) sent to the sites such as safety reporting information, Medical Monitor contact information, and change in company name were also included in this amendment.

## **11. NON-SUBSTANTIAL AMENDMENT 4 (15 NOVEMBER 2013)**

The purpose of the non-substantial amendment (administrative letter) was to notify the Investigators of the following administrative change to Sunovion Pharmaceuticals Inc. Protocol 093-050 (Version 6.0, dated 07 Jun 2013):

Sections 11.1 (ECGs); 11.4.9 (End of Study/Early Termination); Appendix III (Cardiac Safety Monitoring); and Appendix IX (Computerized Systems Used for Source Data): A post-1-year ECG assessment, if performed, should have been over-read.

### List of abbreviations and definition of terms

25-OHD	Serum 25-hydroxyvitamin D
AE	Adverse Event
AEDs	Anti-Epileptic Drugs
ALT	Alanine Aminotransferase
aPTT	Activated Partial Thromboplastin Time
AST	Aspartate Aminotransferase
BMI	Body Mass Index
BP	Blood Pressure
bpm	Beats per Minute
BUN	Blood Urea Nitrogen
eCRF	Electronic Case Report Form
C-SSRS	Columbia-Suicide Severity Rating Scale
ECG	Electrocardiogram
EENT	Eyes, Ears, Nose, and Throat
ESL	Eslicarbazepine acetate
HDL	High Density Lipoprotein
INR	International Normalized Ratio
IPD	Important Protocol Deviation
ITT	Intent-to-Treat
LDL	Low Density Lipoprotein
MADRS	Montgomery-Asberg Depression Rating Scale
MEC	Medical Events Calendar
MedDRA	Medical Dictionary for Regulatory Affairs
N/A	Not Applicable
NTx	N-telopeptides of type I collagen cross-links
PCS	Potentially Clinically Significant
PGI	Patient Global Impression
PT	Prothrombin Time
PTH	Parathyroid Hormone
PTT	Partial Thromboplastin Time
QD	Once Daily
QOLIE	Quality of Life in Epilepsy
SAP	Statistical Analysis Plan
SOC	System Organ Class
SSF	Standardized Seizure Frequency
TEAE	Treatment-Emergent Adverse Event
ULN	Upper Limit of Normal
WHO	World Health Organization

